## 2.1. Multiplicity Adjustment

Multiplicity adjustment procedure will be used to control the overall Type I error rate for the 2 co-primary and 14 key secondary endpoints. Since there are 2 randomizations utilized in the study (i.e., 2 different experiments), the endpoints prior to or at Week 16, and the endpoints related to the randomized withdrawal will each be assigned with a 2-sided significance level of 0.05. The testing procedure begins with the test of superiority of JNJ-77242113 group compared with placebo group in the co-primary endpoints. Key secondary endpoints will only be tested if the co-primary endpoints are significant. The testing strategy is devised based on the expected power and relative importance of the endpoints. If either test of the co-primary endpoints is not significant (i.e.,  $p > 0.05$ ), all subsequent p-values for all the key secondary endpoints will be considered nominal. After testing of the co-primary endpoints, and if both p-values are  $\leq 0.05$ , the testing procedure will continue with superiority tests for the key secondary endpoints.

The endpoints during the first 16 weeks of placebo-controlled period are grouped in 4 tiers. Within each tier, the Bonferroni–Holm’s (Holm S 1979) procedure (see [Figure 2](#) below for an illustration of the full testing procedure) will be used to test all endpoints in that tier with an overall type I error rate of 0.05 (2-sided). If any test within a tier is not significant, the other tests in the same tier could still be declared significant if they meet the Holm thresholds, but the formal testing will stop and all p-values in subsequent tiers will be considered nominal. If all tests within a tier are significant based on Bonferroni–Holm’s procedure, then testing will continue to the next tier.

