In general, all statistical tests will be performed at a significance level of 0.05 (2-sided) unless otherwise specified. Appropriate multiplicity adjustment procedure will be used to control the overall Type I error rate of $\alpha=0.05$ (2-sided) for the primary and key secondary endpoints (see Section 9.3.3). Since there are 2 randomizations utilized in the study (ie, 2 different experiments), the Week 16 endpoints and the endpoints related to the randomized withdrawal will each be assigned with a 2-sided significance level of 0.05. Details will be described in the SAP. No adjustments for multiple comparisons will be made for other secondary endpoints and exploratory endpoints. Nominal p-values for other secondary and exploratory endpoints will be reported but should not be used to infer statistical significance.

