**Figure 2: Testing procedure for the key secondary endpoints during the placebo-controlled period**

Additionally, if the co-primary endpoints are significant, the following endpoints during the randomized withdrawal portion will also be tested using the graphical approach at a 2-sided overall alpha of 0.05 (Figure 3).

- Time to loss of PASI 75, Time to loss of PASI 90
- PASI 75 response at Week 52, PASI 90 response at Week 52

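### The overall two-sided 0.05 stated for the co-primary and all key secondary endpoints holds within each randomization but not study-wide, where the rate can reach about 0.0975

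*SAP*

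**What the plan says.** **The overall claim.** Protocol 9.3.1 promises to "control the overall Type I error rate of $\alpha=0.05$ (2-sided) for the primary and key secondary endpoints". The synopsis (Protocol 1.1) makes the same promise. Protocol 9.3.3 repeats the 0.05 for the co-primary endpoints and its list of key secondary endpoints, which includes the four randomized-withdrawal endpoints. SAP 2.1 sets the scope: "Multiplicity adjustment procedure will be used to control the overall Type I error rate for the 2 co-primary and 14 key secondary endpoints". That sentence names no level, and neither does the matching sentence in SAP 4.1.

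**The allocation.** SAP 2.1 gives its reason as "Since there are 2 randomizations utilized in the study (i.e., 2 different experiments". It then says that the endpoints up to Week 16 and "the endpoints related to the randomized withdrawal will each be assigned with a 2-sided significance level of 0.05". Protocol 9.3.1 says the same: "the Week 16 endpoints and the endpoints related to the randomized withdrawal will each be assigned with a 2-sided significance level of 0.05".

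**The order of testing.** "Key secondary endpoints will only be tested if the co-primary endpoints are significant". After that, the ten endpoints from Week 4 to Week 16 go through four serial tiers with Holm's procedure inside each tier at 0.05. The four withdrawal endpoints "will also be tested using the graphical approach at a 2-sided overall alpha of 0.05" on the same co-primary condition (SAP 2.1, text before Figure 3). They do not wait for Tiers 1 to 4.

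**The concern.** One sentence places all 16 endpoints under a single overall error rate, while the procedure spends 0.05 twice. The second comparison rests on a fresh randomization, so false rejections in the two families are close to independent. They accumulate rather than share one 0.05.

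What is at stake is the meaning of the key secondary claims. SAP 2.1 will declare significance when a multiplicity-adjusted p-value is at or below 0.05. A reader of the Protocol's statement would take all 14 endpoints as protected by one 0.05, which the procedure does not deliver.

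**Working it through.** **Inputs**
- Endpoints (SAP 2.1): Tiers 1 to 4 hold 3 + 3 + 2 + 2 = 10 endpoints and the withdrawal family holds 4, so 14 key secondary endpoints in all.
- Levels (SAP 2.1, Protocol 9.3.1): two-sided 0.05 for each family.
- Co-primary power: above 99% for both together (Protocol 9.5, SAP 5) and above 99.9% for each scenario (Protocol Table 2, SAP Table 9).
- Withdrawal arms: 540 adults x 2/3 x 75% / 2 = 135 per arm, as in those tables.

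**Step 1. Where 0.05 is reproduced**
- *A co-primary null is true (this includes the global null).* No key secondary claim is possible unless that co-primary null is falsely rejected. The chance of any false claim is therefore at most 0.05.
- *Within the Week 4 to 16 family.* Holm inside serial tiers keeps the rate at or below 0.05.
- *Within the withdrawal family.* The text sets the graphical procedure at 0.05 overall.

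**Step 2. Where 0.05 is not reproduced**

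Suppose both co-primaries are truly effective, so that key secondary testing opens with probability above 99%. Suppose also that each family contains a true null that testing reaches. In the first family, Holm's last step uses the full 0.05 once the other hypotheses in that tier and all earlier tiers have been rejected. Then:
- under independence, 1 - (1 - 0.05)(1 - 0.05) = 0.0975;
- with no assumption on dependence, 0.05 + 0.05 = 0.10.

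A simulation of 40,000 trials checked the independence assumption. It used re-randomized responders, outcomes correlated within participant, one true null per family and the co-primary condition taken as met. The rejection rates were 0.0516 and 0.0490 for the two families and 0.098 for either (Monte Carlo standard error √(0.098 x 0.902 / 40,000) = 0.0015). If only one family contains a true null, the rate stays at or below 0.05.

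**Step 3. What splitting alpha would cost**

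The usual pooled-variance formula with n = 135 per arm is

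power = Φ{ [Δ - z √(2 p̄(1 - p̄)/n)] / √([p1(1 - p1) + p2(1 - p2)]/n) }.

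For 60% against 80% at 0.05: (0.2 - 1.960 x 0.0558) / 0.0544 = 1.67, which gives 95.2%, the plan's figure. At 0.025: (0.2 - 2.241 x 0.0558) / 0.0544 = 1.38, which gives 91.6%.

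| Withdrawal / continued | Stated | Recomputed at 0.05 | At 0.025 |
|---|---|---|---|
| 60% / 80% | 95.2% | 95.2% | 91.6% |
| 65% / 85% | 97.0% | 97.0% | 94.5% |
| 70% / 90% | 98.6% | 98.7% | 97.3% |

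The last column assumes that PASI 75 at Week 52 is tested at the family's full alpha. Figure 3 is not visible in the text, so its starting weights are unknown. If that endpoint were tested at half of a 0.025 family level (0.0125), power would be about 87%, 91% and 95%. A 0.025/0.025 split bounds the study-wide rate at 0.05 (0.0494 under independence).

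**The case against.** The strongest reply is that nothing is hidden. In both documents the sentence on overall control is followed closely by the allocation and its reason, two randomizations regarded as two experiments. On that reading, overall means within each experiment, and Step 1 shows that 0.05 then holds. Whether two randomizations in one trial must share one alpha is a matter of position, and the sponsor has stated its own. The Protocol also leaves the detailed procedure to the SAP, where the overall sentence carries no number.

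Most of this stands. The allocation is a legitimate, declared choice. It does not rescue the claim as worded, because Protocol 1.1 and 9.3.3 give one overall 0.05 with no per-experiment qualifier, and the list in 9.3.3 includes the withdrawal endpoints.

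A second reply is that the tests are for superiority. False claims in the drug's favour run at about 0.025 per family, or 1 - 0.975² = 0.049 over both. That softens the practical consequence, but the documents state a two-sided rate.

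A reader might also infer that the chance of a false key secondary claim is nearly doubled in general, or that the primary conclusion is weakened. The documents support neither. The co-primary condition caps the rate at 0.05 whenever a co-primary null is true, and study success rests on the co-primaries alone.

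**Conclusion.** The plan states a single overall two-sided 0.05 that its procedure does not deliver study-wide. Control at 0.05 holds for the co-primary claim, under the global null and within each family. Over all 14 key secondary endpoints the rate can reach about 0.0975, or at most 0.10 without assuming independence.

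These figures are a worst case. They require both co-primaries to be truly effective and each family to contain a true null that testing reaches. If most endpoints truly respond to treatment, the actual rate is lower.

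A reader might conclude that alpha must be split. The documents do not compel that: per-randomization control is a declared design with a rationale, and only the statement attached to it is wrong. Severity is minor to moderate. The primary conclusion, the sample size and study conduct are not affected.

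**What to change.** **Change the wording** in Protocol 1.1, 9.3.1 and 9.3.3 and in SAP 2.1 and 4.1. Replace the overall claim with a statement such as: *Type I error is controlled at two-sided 0.05 within each of the two randomizations, after both co-primary tests succeed; the study-wide rate over all key secondary endpoints can reach about 0.0975 (at most 0.10).* This costs only a less favourable stated figure. The design, sample size and power are unchanged.

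**Only if the sponsor wants to keep the single overall 0.05**, there are two options, each a trade-off:
- *Split 0.025/0.025 between the families.* Week 52 PASI 75 power falls to about 91.6%, 94.5% and 97.3%, assuming that endpoint gets its family's full alpha. The stated minimum of 95% power would then fail in two of the three scenarios and would need rewording. The co-primaries can keep the full 0.05.
- *Test the withdrawal family only after all of Tiers 1 to 4 are rejected.* No alpha is split, but every Week 52 maintenance claim would then depend on all ten earlier endpoints, including itch at Week 4. The documents give no power for those ten endpoints, so this cost cannot be computed from them.

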### Tier 1 (comparison between JNJ-77242113 and placebo group randomized at Week 0)

- PASI 75 at Week 16
- PASI 100 at Week 16
- IGA score of 0 at Week 16

### Tier 2 (comparison between JNJ-77242113 and placebo group randomized at Week 0)

- PSSD symptom score of 0 at Week 16
- $\geq 4$ -point improvement from baseline in PSSD itch score at Week 16

- ss-IGA score of 0 or 1 and  $\geq 2$ -grade improvement from baseline at Week 16

[figure not shown]
Tier 3 (comparison between JNJ-77242113 and placebo group randomized at Week 0)

- PASI 90 at Week 8
- PSSD symptom score of 0 at Week 8

Tier 4 (comparison between JNJ-77242113 and placebo group randomized at Week 0)

[figure not shown]
- PASI 75 response at Week 4.
- $\geq 4$ -point improvement from baseline in PSSD itch score at Week 4

**Figure 2: Testing procedure for the key secondary endpoints during the placebo-controlled period**

Additionally, if the co-primary endpoints are significant, the following endpoints during the randomized withdrawal portion will also be tested using the graphical approach at a 2-sided overall alpha of 0.05 (Figure 3).

- Time to loss of PASI 75, Time to loss of PASI 90
- PASI 75 response at Week 52, PASI 90 response at Week 52

**Figure 3: Testing procedure for the endpoints during the randomized withdrawal period**

The study will be considered successful if the tests for both co-primary endpoints are positive. For all key secondary endpoints specified above, both multiplicity-adjusted and nominal p-values will be provided. Statistical significance will be claimed if the adjusted p-value is  $\leq 0.05$ . No multiplicity adjustments will be made for the other secondary and exploratory endpoints and these statistical testing will be performed at the 2-sided 0.05 significance level. Nominal p-values will be presented.

### 3. ANALYSIS SETS

For purposes of analysis, the following analysis sets are defined in [Table 1](#):

**Table 1: Definition of Analysis Sets**

Population	Description
Enrolled	All participants who signed the ICF
Randomized	All participants who were randomized at Week 0 in the study.
Randomized at Week 24	All participants who were rerandomized at Week 24 in the study.
Full Analysis Set (FAS)	All participants who were randomized at Week 0 in the study.
Per Protocol (PP)	The per protocol analysis set (PP) includes a subset of participants in the full analysis set (FAS) who were in general compliance with the protocol. Compliance is defined as participants in FAS and meet the following criteria: 
 
• Had a total BSA <math>\geq 10\%</math> at the screening and baseline visit.
 
• Had a total PASI score <math>\geq 12</math> at the screening and baseline visit
 
• Had a total IGA score <math>\geq 3</math> at the screening and baseline visit
 
• Had an overall compliance of study treatment at least 80% and <math>\leq 120\%</math> prior to Week 16
 
 Participants with intercurrent events 1 and 2 (section 4.2.2.1.1) will be included in the per protocol analysis set
Safety Analysis Set	All randomized participants who took at least 1 dose of study intervention.
PK Analysis Set	All randomized participants who received at least 1 dose of JNJ-77242113 and had at least 1 valid blood sample drawn for PK analysis after their first dose of JNJ-77242113
Immunogenicity Analysis Set	All randomized participants who received at least 1 dose of JNJ-77242113 and who had at least 1 sample obtained after the first dose of JNJ-77242113 for the detection of antibodies to JNJ-77242113.

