 - Any suicidal behavior in their lifetime that maybe defined as a C-SSRS rating at screening of: Actual suicide attempt, interrupted suicide attempt, aborted suicide attempt, or preparatory behaviors for making a suicide attempt.
8. History of drug or alcohol abuse within 1 year before screening.

Prior/Concomitant Therapy

9. Previously received JNJ-77242113.
10. Experienced primary efficacy failure (no response within 16 weeks) to 1 or more agents directly targeting IL-23 or has had a clinically significant AE to 1 or more agents directly targeted to IL-23.

Note: This criterion does not apply to previous IL-12/23 use.

Prohibited Medication or Class of Medications	Restriction Duration (through End of Study)
11. Agents that deplete B cells: 
 • alemtuzumab or rituximab 	26 weeks prior to the first administration of study intervention
12. Any biologic therapy including but not limited to: 
 • IL-23-inhibitors: guselkumab, tildrakizumab, risankizumab (Additional exclusions apply; see EC 9 and 10). • IL-17 inhibitors: secukinumab, brodalumab, ixekizumab. • IL-12/23 inhibitors: ustekinumab, briakinumab. • TNFα antagonists: adalimumab, infliximab, etanercept, certolizumab, golimumab. • natalizumab • belimumab • abatacept • visilizumab 	12 weeks or 5 half-lives, whichever is longer, prior to the first administration of study intervention

 experimental or investigational therapy 	
Prohibited Medication or Class of Medications	Restriction Duration (through End of Study)

13. Systemic immunomodulating treatments including but not limited to:
 
 methotrexate, azathioprine, cyclosporine A, corticosteroids, cyclophosphamide, tofacitinib, apremilast, deucravacitinib 
Other therapeutic procedures:
 
 phototherapy 
Systemic medications that could affect psoriasis evaluations including, but not limited to:
 
 acitretin, retinoids, herbal treatments, or traditional Taiwanese, Korean, or Chinese medicines 
Nonbiologic experimental therapies or investigational agents
	
4 weeks prior to the first administration of study intervention

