9.2. Analysis Sets

For the efficacy analyses in this study, the FAS will be used according to the participants' assigned treatment to which they are randomized, regardless of the treatment they received. The FAS will include all randomized participants.

Safety analyses will include all randomized participants who received at least 1 administration of study intervention and participants will be analyzed based on the treatment they actually received, regardless of the treatment groups to which they were assigned.

For purposes of analysis, the following analysis sets are defined:

Population	Description
Enrolled	All participants who sign the ICF
Randomized	All participants who were randomized in the study.
FAS	All participants who were randomized in the study.
Per-protocol Analysis Set	A subset of participants in the full FAS who were in general compliance with the protocol elements that could affect the efficacy assessments.
Safety Analysis Set	All randomized participants who take at least 1 dose of study intervention.
PK Analysis Set	All randomized participants who received at least 1 dose of JNJ-77242113 and had at least 1 valid blood sample drawn for PK analysis after their first dose of JNJ-77242113
Immunogenicity Analysis Set	All randomized participants who received at least 1 dose of JNJ-77242113 and who had at least 1 sample obtained after the first dose of JNJ-77242113 for the detection of antibodies to JNJ-77242113.

In addition, select secondary efficacy analyses will also be performed on subpopulations of FAS (eg, participants randomized at Week 24).

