These 2 co-primary endpoints will be compared between the JNJ-77242113 group and the placebo group. In these primary efficacy analyses, data from all randomized participants will be analyzed according to their assigned treatment group. The number and proportion of participants with an IGA score of cleared (0) or minimal (1) and at least a 2-grade improvement from baseline and PASI 90 response at Week 16 will be summarized for each treatment group.

The co-primary endpoints will be analyzed using the primary estimand. Participants with ICEs 1 or 2 before Week 16 will be considered as non-responders at Week 16. For participants with ICE 3, observed data after this ICE will be utilized in the analysis. For participants experiencing multiple ICEs, an ICE 2 will override an ICE 3.

After accounting for the ICEs for the primary estimand, participants with missing data for the co-primary endpoints at Week 16 will be considered as non-responders.

To address the primary objective, a 2-sided ($\alpha=0.05$) CMH chi-square test stratified by age group, baseline weight category for adults, and geographic region will be used for the co-primary endpoints.

The study will be considered positive if the JNJ-77242113 group is significantly different from the placebo group for both co-primary endpoints. Both co-primary endpoints will be tested at a 2-sided α level of 0.05. If at least one of the comparisons is not significant at the 2-sided α level of 0.05, the co-primary endpoints will be considered not significant.

To examine the robustness of the primary endpoint analyses, additional analyses will be conducted using supplemental estimands; these analyses will be described in the SAP. In addition, per-protocol analyses will be performed for the co-primary endpoints using the per-protocol population, which includes participants who are generally compliant with the protocol. To evaluate the consistency of the efficacy, subgroup analyses of the co-primary endpoints based on

demographics (eg, adolescents versus adults), baseline disease characteristics and previous psoriasis medications and therapies will be performed.

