### **6.3. Appendix 3 Protocol Deviations**

In general, the following list of major protocol deviations may have the potential to impact participants' rights, safety or well-being, or the integrity and/or result of the clinical study. Participants with major protocol deviations will be identified prior to database lock and the participants with major protocol deviations will be summarized by category.

- Developed withdrawal criteria but not withdrawn
- Entered but did not satisfy criteria
- Received a disallowed concomitant treatment
- Received wrong treatment or incorrect dose
- Other

A listing of participants with major protocol deviations will also be provided by randomized treatment group.

QTL parameters and thresholds are defined and will be monitored in this study. QTL parameters will be summarized. More details are described in the Integrated Analytical Risk-Based Monitoring Plan.

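### The SAP's four per-protocol criteria do not remove wrong-treatment, washout or disease-form deviations, so its compliance test is narrower than the protocol's definition

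*SAP*

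**What the plan says.** Protocol Section 9.2 describes the per-protocol set as "A subset of participants in the full FAS who were in general compliance with the protocol elements that could affect the efficacy assessments". Section 9.3.2 commits to its use: "per-protocol analyses will be performed for the co-primary endpoints using the per-protocol population, which includes participants who are generally compliant with the protocol".

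SAP Table 1 repeats the idea of general compliance but drops the reference to elements that bear on efficacy. It then fixes the meaning: "Compliance is defined as participants in FAS and meet the following criteria". Four criteria follow:

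- BSA of at least 10% at screening and baseline
- PASI of at least 12 at both visits
- IGA of at least 3 at both visits
- treatment compliance from 80% to 120% before Week 16

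No phrase leaves the list open. One inclusion rule is added: "Participants with intercurrent events 1 and 2 (section 4.2.2.1.1) will be included in the per protocol analysis set".

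SAP Appendix 6 defines compliance as tablets taken divided by tablets due. SAP Appendix 3 has a major-deviation category "Received wrong treatment or incorrect dose" and another for participants who entered without satisfying the criteria. These deviations are identified before database lock, then summarised and listed; no rule connects them to the per-protocol set. SAP Section 4.2.3.4 applies the main-analysis rules of Section 4.2.3.1 to the per-protocol analysis, so participants are counted in the arm they were assigned.

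**The concern.** A per-protocol analysis should show the effect in people who were selected and treated as planned. Three kinds of deviation that bear directly on PASI and IGA pass all four checks:

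- **Wrong study treatment.** A full tablet count from a wrong kit scores as compliant, and the participant is analysed under the assigned arm.
- **Washout breach.** Exclusion criterion 13 covers, among others, "Systemic medications that could affect psoriasis evaluations including, but not limited to", and criterion 14 describes topical treatments in the same way. That is close to the protocol's own test for the per-protocol set, yet no washout is in the SAP list.
- **Disease form.** Inclusion criterion 2 (plaque psoriasis diagnosis) and exclusion criteria 1 and 2 (nonplaque and drug-induced forms) are also absent.

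What is at stake is how informative the supportive analysis of the two co-primary endpoints is. If these deviations stay in, agreement with the FAS result says less about robustness to them than a reader would assume.

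**Working it through.** **The plan's own figure.** Protocol Section 9.5 states >99% power for both co-primary endpoints. The inputs are 200 placebo and 400 active participants, two-sided alpha 0.05, IGA 0/1 rates of 8% and 64%, and PASI 90 rates of 5% and 59%. With Δ the difference and p̄ the pooled rate:

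power = Φ[(Δ − 1.96·SE0)/SE1], where SE0 = √[p̄(1−p̄)(1/400 + 1/200)] and SE1 = √[pA(1−pA)/400 + pP(1−pP)/200].

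- IGA 0/1: p̄ = (256 + 16)/600 = 0.453; SE0 = 0.0431; SE1 = 0.0307; (0.56 − 0.0845)/0.0307 = 15.5.
- PASI 90: p̄ = (236 + 10)/600 = 0.410; SE0 = 0.0426; SE1 = 0.0290; (0.54 − 0.0835)/0.0290 = 15.7.

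Both give power >99.9%, so the stated figure is reproduced. The documents give no size or power for the per-protocol set.

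**Which deviations the SAP removes.**

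| Deviation | Caught by the four criteria? | Caught elsewhere? |
|---|---|---|
| Wrong kit, full tablet count | No. Weeks 0 to 16 are 16 × 7 = 112 tablets; 112/112 = 100% whichever product was taken | No. It is not an intercurrent event; listed as a major deviation only |
| Therapy stopped before first dose but inside the washout | Only if residual effect takes BSA, PASI or IGA below threshold at screening or baseline | Not plainly. Intercurrent event 2 is the initiation of other therapy (SAP Table 2) |
| Nonplaque or drug-induced psoriasis | No | No. Listed as a major deviation only |

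**Size of the wrong-treatment effect.** Let fA and fP be the shares of the active and placebo arms who took the other arm's treatment. Assume that they respond as that other arm does at Week 16. The expected difference falls by (fA + fP)·Δ. With the same share f in both arms, it becomes Δ(1 − 2f).

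| f in both arms (assumed) | Participants (active, placebo) | IGA 0/1 difference | PASI 90 difference | Loss in points (IGA, PASI 90) |
|---|---|---|---|---|
| 0% | 0, 0 | 56.0 | 54.0 | 0, 0 |
| 1% | 4, 2 | 54.9 | 52.9 | 1.12, 1.08 |
| 3% | 12, 6 | 52.6 | 50.8 | 3.36, 3.24 |
| 10% | 40, 20 | 44.8 | 43.2 | 11.2, 10.8 |

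Power stays above 99.9% even at 10%. If crossed participants move only a fraction k of the way to the other arm's response, each loss is multiplied by k.

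**Cost of a stricter set.** Removing 20% (320 active, 160 placebo) multiplies both standard errors by √(1/0.8) = 1.118. The arguments become (0.56 − 0.0945)/0.0343 = 13.6 for IGA 0/1 and (0.54 − 0.0933)/0.0324 = 13.8 for PASI 90. Power is still above 99.9%.

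No figure can be derived for washout or disease-form breaches, because the documents give neither their frequency nor their effect on response.

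**The case against.** The protocol asks only for general compliance, names no deviation that must be excluded, and leaves detail to the SAP. The SAP has made a loose definition operational, and the two documents do not flatly contradict each other. That stands: a reader might infer that the SAP substitutes a different analysis for the one the protocol promised, but the text supports only that its list is too short for the protocol's own test.

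No decision rests on the analysis. Success is judged in the FAS on the two co-primary tests, and the per-protocol analysis carries no alpha. Deviations will be listed by randomised arm, so a reader can see them. Crossed treatment shrinks the difference, which is the conservative direction. All of this stands and limits the point to a supportive analysis.

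On washouts, it is tempting to say that residual therapy inflates response. The documents do not show this. Response is measured against baseline; prior therapy that suppressed baseline disease and then wore off could lower response. The severity thresholds also remove some participants with strong residual effect. For therapy continued on study, SAP Appendix 7 words intercurrent event 2 in terms of therapy used for psoriasis, which may reach such cases. The gap is clearest for therapy stopped before the first dose.

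Finally, not every item in exclusion criteria 9 to 14 is shown to affect efficacy. Criterion 10 includes a past adverse event on an IL-23 agent, and criterion 12 reaches biologics such as belimumab and visilizumab. A blanket exclusion would go beyond the protocol's test.

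**Conclusion.** The point holds for the supportive per-protocol analysis of the co-primary endpoints. The four SAP criteria leave in wrong-treatment, washout and disease-form deviations, and no other SAP rule takes them out.

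The quantified part is dilution from wrong treatment: about 1.1 points for each 1% crossed in both arms, hence about 1.1 to 3.4 points at 1% to 3%. It rests on the planning response rates, an assumed deviation rate, and a full swap lasting to Week 16. It is an upper bound for a given rate, because kits are dispensed at Weeks 0, 2, 4, 8 and 12 and one wrong kit need not mean a full swap. Washout breaches could bias response in either direction.

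A reader might also infer that the primary conclusion is at risk, or that the per-protocol set will be almost the same as the FAS. The documents support neither. The primary FAS analysis, alpha and power are unaffected, and how close the two sets are depends on data not yet seen.

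**What to change.** In SAP Table 1, add two per-protocol criteria:

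1. No wrong-treatment deviation through Week 16. The Appendix 3 category joins wrong treatment with incorrect dose, so the criterion should name the wrong-treatment part.
2. No violation of inclusion criterion 2, exclusion criteria 1 and 2, exclusion criterion 9 (prior JNJ-77242113), or the washouts in exclusion criteria 12 to 14 for therapies that could affect psoriasis evaluations. The psoriasis-active therapies should be named; the list in Protocol Section 6.9, repeated in SAP Appendix 7, is a ready starting point.

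State that membership is determined from blinded data before the Week 24 database lock. Keep the rule that participants with intercurrent events 1 and 2 remain in the set.

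The change is SAP wording only. Major deviations are already identified before lock, so no new data are needed. The downside is a slightly smaller per-protocol set, which the power check above shows is affordable.
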